#### LIST OF ABBREVIATIONS AND RELEVANT DEFINITIONS

ACT	Active Cancellation of Tremor
ADL	Activities of Daily Life
AE	Adverse Event
ANOVA	Analysis of Variance
AVG	General Data Protection Regulation; in Dutch: Algemene Verordening
	Gegevensbescherming
ССМО	Committee on Research Involving Human Subjects; in Dutch: Centrale Commissie
	Mensgebonden Onderzoek
CE	Conformité Européenne
CIP	Clinical Investigation Plan
CRF	Case Report Form
DBS	Deep Brain Surgery
DOF	Degree of Freedom
DSMB	Data Safety Monitoring Board
D-QUEST	Dutch Quebec User Evaluation of Satisfaction with Assistive Technology
EFE	Elbow Flexion/Extension
EPD	Electronic Medical Record; in Dutch Elekronisch Patiëntendossier
FFE	Finger Flexion/Extension
FPS	Forearm Pronation/Supination
FTM	Fahn-Tolosa-Marin
PSP	Progressive Supranuclear Palsy
GKT	Gamma Knife Thalamotomy
GGZ	Mental Health Care; in Dutch: Geestelijke Gezondheidszorg
IB	Investigator's Brochure
IFU	Instructions for Use
IMDD	Investigational Medical Device Dossier
IMU	Intertial Measurement Unit
METC	Medical research ethics committee (MREC); in Dutch: medisch-ethische
	toetsingscommissie (METC)
MS	Multiple Sclerose
MSA	Multiple System Atrophy
NCCIH	National Center for Complementary and Integrative Health

PC	Personal Computer
QOL	Quality of Life
SAE	Serious Adverse Events
SIER	Shoulder Internal/External Rotation
TETRAS	The Essential Tremor Rating Assessment Scale
TMD	Tuned Mass Dampers
WFE	Wrist Flexion/Extension
WMO	Medical Research Involving Human Subjects Act; in Dutch: Wet Medisch-
	wetenschappelijk Onderzoek met Mensen
WRUD	Wrist Radial/Ulnar Deviation

## **SUMMARY**

**Rationale:** Essential Tremor (ET) is the *most common movement disorder* affecting approximately 1% of the general population and about 5% of the population over 65 years. ET affects fine motor control of the hands and has functional impact, impairing daily activities such as writing, drinking or dressing. Current treatment options have limited effects on tremor, cause side-effects or are task specific. Therefore, the STIL orthosis is developed; a non-invasive passive anti-tremor orthosis that suppresses the tremor in daily life and is easy to wear. The orthosis needs to be tested on patients to validate the effectiveness of the orthosis. In this study the effect of the orthosis on tremor severity, patient satisfaction and product safety will be assessed.

## **Objectives**:

**Primary Objectives:** 

- To evaluate the effects of the STIL anti-tremor orthosis on tremor severity in ET patients with an invalidating forearm tremor.
- To evaluate the effects of the STIL anti-tremor orthosis on tremor amplitude in ET patients with an invalidating forearm tremor.

Secondary Objectives:

- To assess patient satisfaction with regards to the usability and comfort of the STIL anti-tremor orthosis.
- To assess the possible adverse effects of the STIL anti-tremor orthosis.

**Study design:** Single-blind randomized crossover study.

**Study population:** ET patients over 18 years old with an invalidating forearm tremor. **Intervention**: Tremor data will be collected in three conditions: without orthosis (baseline), with orthosis (intervention) and with a sham-device. The order of the modes will be randomly assigned. The investigational device uses the principle of applying external joint damping as its working principle. The sham-device looks and weights the same as the investigational device, however it has no damping elements to suppress the tremor.

**Main study parameters/endpoints:** The primary study parameter is tremor severity measured using the TETRAS scale and the co-primary study parameter is tremor amplitude.

A secondary parameter is patient satisfaction using D-QUEST, another secondary parameter is product safety using NCCIH's Adverse Events Report Form.

## Nature and extent of the burden and risks associated with participation, benefit and group

**relatedness:** The burden associated with participation is low. Participation includes filling out a questionnaire and a hospital visit of maximum one hour to check for eligibility. Once included, the assessment with orthosis in the hospital will take another 30 minutes to one hour. No therapeutic effects are expected; the orthosis is expected to suppress the tremor when being worn. This effect is not expected to last after detaching the orthosis. Based on the exhaustive risk analysis, only minimal risks can be associated with this study. Patients are not at high risk; the two devices only interact with intact skin for a maximum of 30 minutes each (one hours in total) and precautionary measures are taken in case the orthosis does not function as expected.

## 1. INTRODUCTION AND RATIONALE

Essential Tremor (ET) is the *most common movement disorder* affecting approximately 1% of the general population and about 5% of the population over 65 years. ET is characterized by a (mostly symmetrical) tremor of the upper limbs, sometimes involving the head and more rarely the voice, trunk and legs . The tremor is both postural and kinetic, indicating that the tremor occurs during voluntary movement and when the limb is positioned against gravity. ET affects fine motor control of the hands and has *functional impact*, impairing daily activities such a writing, drinking, or dressing . These impairments may also have *social impact*; patients are often ashamed of their inability to participate in social of working activities, leading to avoidance of social events.

There are several ways to treat ET. *Medication* (propranolol or primidone) is usually tried first to control tremor, but many patients experience side effects and in most cases the tremor will not completely disappear . Stereotactic surgery is another widely used treatment, of which *deep brain stimulation* (DBS) used to be the golden standard . DBS can reduce the tremor, but is not applicable for every patient . Moreover, side effects are reported, including paresthesia, dystonia, gait, balance disturbance and ataxia . Besides, hemorrhage and infection can occur due to craniotomy . Another stereotactic surgery is *Gamma Knife Thalamotomy* (GKT)  which creates a lesion in the brain by delivering external radiation. It aims to reduce the tremor, by destroying the cells that are involved in the tremor origination . However, like DBS, this surgery is not suitable for every patient and since it is invasive, not many patients are willing to undergo such a treatment.

The treatments mentioned above target the cause of the disease, while another approach is to suppress the symptoms. Nowadays, tremor suppression techniques are found in *orthotics*. These are devices which mechanically attenuate or dissipate forearm or wrist tremors that have made their upswing in recent years , but do still not provide a practical solution for everyday use. The problem is that often active orthoses rely on actuators coupled to a signal transmission system, resulting in a heavy and unwieldy device . Other alternative solutions are designed for specific tasks, such as eating with a spoon (e.g., Liftware Spoon).

Tremor occurs in all parts of the upper extremity, most present in the:

- shoulder internal/external rotation (SIER)
- elbow flexion/extension (EFE)
- forearm pronation/supination (FPS)
- wrist flexion/extension (WFE)
- wrist radial/ulnar deviation (WRUD)
- finger flexion/extension (FFE)

The currently available passive devices often only tackle suppression in a single degree of freedom (DOF). Strong evidence is found that suppressing a single DOF will not provide relief for tremor patients .

This indicates that current treatment options have limitations. Therefore, the STIL anti-tremor orthosis is developed; a non-invasive, passive, anti-tremor orthosis that suppresses tremor in multiple relevant DOFs to provide relief in daily life and is easy to wear. A prototype of the orthosis is depicted in Figure 1.

*Figure 1*: Rendered image of the STIL anti-tremor orthosis. The medical device suppresses tremor in the forearm by applying additional damping to the wrist flexion/extension (WFE) and the forearm pronation/supination (FPS).

The working mechanism of the orthosis makes use of two passive dampers which exert a damping torque to the wrist and forearm joints. The dampers are designed to restrain high angular velocity more than slower angular velocity. As such, wrist flexion/extension (WFE) and forearm pronation/supination (FPS) tremor are suppressed by the dampers. Wrist radial/ulnar deviation (WRUD) is suppressed since the orthosis restricts this motion in general. In this manner, high frequency involuntary movement in the forearm, such as tremor, is suppressed

but voluntary motion is still allowed. By suppressing the tremor, activities of daily life (ADL) will improve, as well as participation in social activities.

Market research is performed to take patients' interests and needs into consideration. The results showed a high willingness to adopt to a wearable device for tremor suppression, regardless of the attention that the device possibly attracts. This portrays the dissatisfaction of the current treatment and situation, and the need for a more suitable alternative.

The anti-tremor mechanism has not yet been evaluated in a clinical environment. Also, patient satisfaction with regards to STIL's anti-tremor orthosis is another factor that needs to be evaluated. User involvement is important in this stage of product design and development. In this way patients' feedback will be taken into account before the final product will get on the market. Altogether, this stresses the need for a study in which the orthosis is evaluated on patients, which we aim to do in the present study.

## 2. OBJECTIVES

## 2.1 Primary Objectives

The primary objective of this clinical investigation is to assess the performance of the orthosis, divided over two co-primary objectives:

- 1. To evaluate the effect of the STIL anti-tremor orthosis on tremor *severity* reduction in Essential Tremor patients with an invalidating forearm tremor.
- 2. To evaluate the effect of the STIL anti-tremor orthosis on tremor *amplitude* reduction in Essential Tremor patients with an invalidating forearm tremor.

The co-primary objectives have two endpoints. The endpoint of the first primary objective is the assessment of the TETRAS scale by a trained neurologist(s). The expectation is that the orthosis will reduce tremor *severity* by one measure on the TETRAS scale (e.g. from severe to moderate). The endpoint of the second primary objective is achieved by measuring arm motion with an IMU sensor. The expectation is that the orthosis will reduce tremor *amplitude* by more than 60%.

Together, the primary endpoints give a comprehensive evaluation of the performance of the device.

## 2.2 Secondary Objectives

Apart from performance objectives, the intervention with the orthosis shall also be assessed on usability and comfort and safety with two primary objectives:

- 1. To assess patient satisfaction with regards to the usability and comfort of the STIL antitremor orthosis.
- 2. To assess possible adverse effects of the STIL anti-tremor orthosis.

The endpoint of the first secondary objective is the Dutch version of the Quebec user evaluation of satisfaction with assistive technology (D-QUEST) questionnaire, providing a subjective outcome of the usability and comfort of the orthosis from the patient's perspective. The endpoint of the second secondary objective is a listing of (possible) adverse effects, observed either by the investigator and noted down in a (S)AE report form, or as mentioned by the patient in de D-QUEST questionnaire.

Together, the secondary endpoints provide an assessment on safety, comfort and usability of the device.

The health-related quality of life (QoL) will also be evaluated, as this could influence satisfaction from the secondary objective.

## 3. STUDY DESIGN

This single-blind randomized crossover study will take place at the neurology department of the Reinier de Graaf hospital in Delft.

Tremor severity and amplitude will be measured in three conditions: without orthosis (*baseline*), with a sham-device (*sham*), and with the anti-tremor orthosis (*intervention*). The order of the devices will be randomly assigned by a software specifically designed to aid the investigation. The sham device looks and weighs the same as the anti-tremor orthosis, however it does not contain the working mechanisms used to suppress the tremor. The patient does not know the order of the devices. In this way, single-blinding is guaranteed.

Health-related QoL will be assessed prior to the start of testing with the orthosis, as it could possibly intervene with patient satisfaction. Tremor severity and satisfaction with the devices will be assessed after using a device.

A schematic overview of the study design is depicted in Figure 2. Patient inclusion will be evaluated based on the criteria described in Section 4. Patient inclusion is executed in two steps: first by evaluation of a questionnaire which the patients fill in remotely, and second by a physical evaluation during an appointment in the hospital.

During this appointment in the hospital, patients are asked to perform 7 movement tasks. The movement during tasks will be registered with motion sensors and video-recorded to allow evaluation afterwards.

When the principal investigator is confident that a patient is eligible and he/she is willing to participate, the next part of the appointment – i.e. testing the orthosis and the sham-device – will follow directly. The earlier obtained results of the 7 tasks will be used as the baseline condition. If the principal investigator is unsure if the patient is eligible, the patients is sent home after max. 1 hour. Additional video analysis will determine if the patient is eligible to continue with testing the orthosis. If so, the patient is invited for a second appointment of max. 2 hours, where again is started with 7 movement tasks without orthosis (baseline), followed by testing the orthosis and the sham device in random order.

This protocol allows for minimal impact on the patients, since only a single visit of two hours to the hospital could be sufficient. The study has started in March 2022 and should be finished by December 2022.

Figure 2: Flowchart of the study design

CONFIDENTIAL

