## 4.2 Inclusion criteria

Based on comparable studies , the following inclusion criteria are defined for participants:

- Participant is at least 18 years of age.
- Willing to sign the informed consent.
- Diagnosed with Essential Tremor.
- Significant disability due to forearm tremor. A minimum subscore of 30 across all upper limb items, scored for the most affected arm/hand with the Bain and Findley ADL scale .
- A tremor severity subscore of 13 or higher in the arm/hand as measured by 7 rated TETRAS tasks. The posture and ADL tasks are assessed using the scale used to assess the upper limb tremor.
- A predominant FPS and/or WFE tremor with minor influence of SIER, EFE and FFE tremor according to the principal investigator's judgement. When no clear judgement can be formed, assessment of DOFs using TETRAS' upper limb tremor scale can be performed using the method in Appendix I.

Note: a predominant FPS and/or WFE tremor with the absence of a SIER, EFE and FFE is defined as: a rating below 1,5 in the SIER in a maximum of two rated TETRAS tasks AND below 2 in the EFE and FFE in a maximum of two rated TETRAS tasks

The amplitude of the postures and ADL tasks is rated peak-to-peak using TETRAS' upper limb tremor scale. More thorough instructions on how the tremor DOFs are assessed are included in Appendix I.

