## 4.4 Sample size calculation

The first primary outcome measure, the TETRAS score, is normally distributed . The seven performed tasks are rated on a 0-4 scale of which three with halve points. When the scores are summed, the total outcome has a resolution of 3\*9 + 4\*5 = 47 steps, and can be seen as a continues outcome measure.

The second primary outcome measure, IMU measurements, is continuous and has a logarithmic relationship with respect to the TETRAS scale and is therefore lognormally distributed. After applying a logarithmic transformation, the IMU data will also be normally distributed .

Given the above characteristics of the outcome measures (see Section 2) and the crossover study design (see Section 3), the sample size has been calculated with G\*power using a two-tailed matched pair t-test.

G*Power 3.1.9.7	-	- 🗆 🗙	1		
File Edit View Tests Calculator Help					
Central and noncentral distributions Protoc	ol of power analyses				
0.3 0.2 0.1 0 -2 0 Test family Statistical test	critical t = 2.74438	6			
t tests V Means: Difference betwee	een two dependent means (matched pair	s) ~			
Type of power analysis			Fr	om differences	
A priori: Compute required sample size - gi	ven $\alpha$ , power, and effect size	~		Aean of difference	0
Input Parameters	Output Parameters			SD of difference	1
Tail(s) Two	
 
Noncentrality parameter δ
 
	3.6660606			
Determine => Effect size dz 0.800	0000 Critical t	2.7443764	Fr Fr	om group parameter	s
α err prob 0.	0125 Df	20		Mean group 1	14
Power (1-β err prob)	0.8 Total sample size	21		Mean group 2	10
	Actual power	0.8100407		SD group 1	5
				SD group 2	5
			Correlatio	n between groups	0.5
			Calculate	e Effect size dz	0.8
			Calcula	ate and transfer to m	ain window
					Close
	X-Y plot for a range of values	Calculate			

Figure 3: G\*Power calculation

Four studies, in which the effect of an active hand device on tremor amplitude is investigated, are used to estimate the effect size. Two of these studies did not use mechanical suppression, but reduced the tremor by means of nerve or muscle stimulation. More information about these studies can be found in Section 6.2 and 6.3.

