- Steadi-One; a mechanical device which uses of fluids for reducing amplitude of motions . Results show those patients who improved by kinematic analysis had a 0.81-point score clinical improvement. There was a 0.57-point improvement in dynamic tasks based on the Fahn-Tolosa-Marin clinical rating scale (FTM) .
- The study of Lin et al. (2018) evaluated the CALA wrist device that used nerve stimulation to reduce hand tremor. This study showed a tremor amplitude reduction of 60% ± 8.4% (n = 23) which was significantly greater in the treatment than in the sham group .
- The Liftware Spoon, a handheld assistive device which also makes use of active cancellation of tremor, reduced the tremor amplitude with 73% ± 13% (n = 11) .
- The out-of-phase wrist device that uses electrical stimulation of antagonistic muscle of Maneski et al (2011) showed a significant reduction in tremor amplitude of 67% ± 13% (n = 7)
   .

Given the fact that the effects showed in other anti-tremor device studies were large, and the patients only benefit from a device that has a large effect on their tremor, the effect size d 0.8 was chosen .

An example calculation where the orthosis reduces 4 points (out of 28 total) on the TETRAS scale, assuming a standard deviation of 5 for both groups, generates this effect size of 0.8 (see Figure 3).

In total, 4 conditions will be compared with 2 different outcome measures; baseline vs. intervention (TETRAS), sham vs. intervention (TETRAS), baseline vs. intervention (IMU data) and sham vs. intervention (IMU data).

Taking into account a worst-case scenario of type 1 errors accumulation over the 4 testing conditions, a Bonferroni correction of alpha = 0.05/4 = 0.0125 is used.

The power value of 0.8 has been used, since this value is common practice in medical literature.

Using the above-mentioned parameters, it can be concluded that a minimum of 21 patients is needed. In order to compensate for possible drop-outs (10%), 25 patients will be included for this clinical investigation.

If the data is not normally distributed (after log compensation), unlike described in literature, the statistical analyses can also be performed by means of 4 Wilcoxon matched pair tests. This has no consequences for the sample size, since the sample size analysis in such case will result in 22 patients.

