## 3. Inclusion of patients

The next step requires a visit to the hospital; this appointment will last for a maximum of one hour and takes place at the neurology department of the Reinier de Graaf hospital in Delft. Time will be taken to make the patient feel at ease, to make sure that the patient is not nervous or stressed which may increase tremor severity. The patient is allowed to drink something at this moment (caffeine and alcohol free). This is also when the procedure will be explained and allows a moment for the patient to ask questions. During this appointment, patients will be asked to perform the 7 selected TETRAS tasks (see Section 7.3.4), which will be videorecorded. Two synchronized webcams will record the tasks, which will be done for both the left and the right side. The IMU sensors will be attached on the wrist and hand to record the motion data (see Section 7.3.3). If the patient seems suitable for testing the orthosis, the IMU and video recordings will be used to indicate the tremor severity of the patient without orthosis (baseline).

The hand and upper arm circumference will also be measured by the investigator, these can later be used to select the correct size of the orthosis (S, M, L). If, after this step, the judgement can be drawn that the patient is suitable for the study, meaning that all inclusion- and exclusion criteria (see Section 4.2 and 4.3) are fulfilled, the assessment with the orthoses will directly follow. In preparation for this intervention, it will be determined which arm will be tested, including which size. If only one side turns out to be eligible (left or right), then that side shall be used to test the intervention. If both sides are eligible, the dominant arm as defined by the patient shall be used.

After the TETRAS tasks in baseline condition, the video recordings will be assessed by the principal investigator, where tremor severity and dominant tremor DoF is evaluated.

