## 7.3.5 Cross-over test procedure

The study is designed to be a cross-over study, where baseline is compared to the intervention, and sham is also compared to the intervention.

The assessment procedure in Sections 7.3.3 and 7.3.4 will therefore be repeated 3 times, like is depicted in Figure 4.

The first condition is the baseline condition without orthosis. In the second and third condition, the sham device and anti-tremor orthosis will be tested, in randomized order. The CRF software determines the randomization.

The investigator will fasten the orthosis as explained in Section 6.5. The IMU sensors can stay attached at the same places as in the baseline condition.

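### For same-day patients the qualifying TETRAS score is reused as baseline, so regression to the mean biases the primary baseline vs intervention TETRAS test toward the device

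*Protocol*

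**What the plan says.** Protocol Section 4.2 makes eligibility depend on the outcome scale itself: "A tremor severity subscore of 13 or higher in the arm/hand", from the seven rated tasks.

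Protocol Section 3 describes two paths. If the principal investigator is confident of eligibility, device testing follows at the same appointment, and "The earlier obtained results of the 7 tasks will be used as the baseline condition". If not, the patient goes home, the video is reviewed, and an eligible patient returns and repeats the seven tasks without a device. Section 7.3.1 (step 3) confirms that on the same-day path the screening IMU and video recordings serve as baseline. It adds that if only one arm qualifies, that arm is the one tested.

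On order, Section 7.3.5 says "The first condition is the baseline condition without orthosis". Sections 3, 7.2 and 7.3.5 randomise only sham and orthosis. The Summary lists all three conditions and then says "The order of the modes will be randomly assigned".

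Section 4.4 names four primary comparisons: baseline vs intervention and sham vs intervention, each on TETRAS and on IMU amplitude. For these, "a Bonferroni correction of alpha = 0.05/4 = 0.0125 is used".

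**The concern.** Selecting patients on a noisy score and then using that same score as the comparator gives a non-zero expected difference when there is no effect. A score of 13 or more can reflect a severe tremor, or a moderate one that happened to be worse (or was rated more generously) in that half minute. The later measurement with the device regains only the true part. The paired t-test in Section 9.1 does not correct for this, and a larger sample does not remove it.

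The bias favours the device in a primary TETRAS test. The protocol does not say how many of the four tests must succeed. A Bonferroni split is the correction used when any one of them may support a claim, so a result on the baseline contrast alone could be read as success.

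Two related weaknesses go with it. Baseline is a selected value in same-day patients and a fresh one in second-visit patients. And because baseline is always first, condition is confounded with time on both paths.

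**Working it through.** **Reproducing the plan's own figure.** Inputs from Section 4.4: example means 14 and 10, SD 5 per condition, correlation 0.5, and a sample size found "using a two-tailed matched pair t-test" at two-sided alpha 0.0125. "The power value of 0.8 has been used".

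- SD of difference = √(25 + 25 − 2·0.5·25) = 5, so dz = 4/5 = 0.8.
- At n = 21 the noncentrality is 0.8·√21 = 3.666, the critical t is 2.744 and the power is 0.810. At n = 20 the power is 0.783. The stated 21 is correct.

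**Expected bias on TETRAS.** Let the screening score X₁ and a later score X₂ under the same true state be normal with mean μ, SD σ and test-retest correlation r. Given X₁ ≥ c,

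E[X₁ − X₂] = (1 − r)·σ·λ, with λ = φ(a)/(1 − Φ(a)) and a = (c − μ)/σ.

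From the protocol: c = 13 (Section 4.2) and σ = 5 (Section 4.4). Not in the protocol, and assumed: μ from 11 to 15 in the patients screened, r from 0.7 to 0.9. The 0.5 in the sample-size figure is a correlation between conditions, not a test-retest figure.

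- μ = 11: a = 0.4, λ = 1.069. Bias = 0.3·5·1.069 = 1.60 at r = 0.7, and 0.1·5·1.069 = 0.53 at r = 0.9.
- μ = 14: a = −0.2, λ = 0.675. Bias = 1.01 at r = 0.7, 0.68 at r = 0.8 and 0.34 at r = 0.9.
- μ = 15: a = −0.4, λ = 0.562. Bias = 0.84 at r = 0.7 and 0.28 at r = 0.9.

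The range is 0.28 to 1.60 points. Against the 4-point planning effect that is 0.28/4 = 7% to 1.60/4 = 40%.

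**False-positive rate.** This comes from simulated trials of n = 21 with no device effect and no time trend, using a two-sided paired t-test at 0.0125.

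| Screened mean, reliability | All same-day | Half return at random |
|---|---|---|
| 11, 0.7 | 0.26 | 0.05 |
| 14, 0.8 | 0.06 | 0.02 |
| 15, 0.9 | 0.03 | 0.015 |

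Almost all of these rejections favour the device. With half the patients on the second-visit path the mean bias halves, to about 0.15 to 0.8 points (for example 0.68 to 0.34 at μ = 14, r = 0.8).

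**The sham contrast.** Sham and orthosis are both measured after selection and in random order. In simulation under the null, the mean difference between two post-selection measurements was about zero, and rejections were about 0.6% in each direction, which is the nominal rate. The same holds for a baseline measured again after inclusion, leaving order effects aside.

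**Power of the fallback.** Two tests at 0.05/2 = 0.025, n = 21, dz = 0.8: power 0.883, against 0.810 at 0.0125.

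**The case against.** Several points against the concern have force.

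- **The size rests on assumptions.** The protocol gives no test-retest reliability, no mean for the screened population and no share of same-day patients. The 0.26 needs a mean below the cut-off, reliability of 0.7 and no second visits. Patients are pre-screened on the Bain and Findley scale (Sections 4.2 and 7.3.1), which makes a low mean less likely, and the only mean in the plan is the 14 of the worked example. SD 5 is the plan's value for the compared conditions, not for a screening population. All this stands, and it is why a range is given. It does not change the direction. Nor is return likely to be random: if same-day patients are those well above 13, their effective cut-off is higher and their own regression larger.
- **An unbiased primary contrast already exists.** Sham vs intervention is primary on both endpoints. This stands. A reader might infer that the trial as a whole is invalid, and the documents do not support that.
- **Both baseline contrasts.** A reader might infer that the IMU comparison is biased to the same extent. Selection is on TETRAS. IMU error is shared only as far as both reflect the same 30-second performance, and nothing in the protocol allows a figure.
- **Order.** A reader might infer that taking baseline first also favours the device, because time is set aside to "make sure that the patient is not nervous or stressed which may increase tremor severity". That sentence describes a safeguard. Settling or practice would favour the device and fatigue would oppose it, so the sign is unknown.
- **The Summary.** A reader might see a rule to randomise all three conditions. The body of the protocol consistently randomises only the two devices, so the Summary is loosely worded.

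**Conclusion.** The concern holds for the primary baseline vs intervention TETRAS test. On the same-day path, which Section 3 presents as potentially sufficient for a patient's whole participation, selection and baseline are the same measurement, and regression to the mean favours the device.

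Under the assumed mean and reliability, the worst case is a false-positive rate about 20 times nominal (0.26/0.0125 = 20.8). The mildest all-same-day case is about double (0.027/0.0125 = 2.2). With half the patients returning at random, the rate stays at or above nominal, up to about 0.05. Reliability above 0.9 would shrink the bias further.

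For IMU amplitude the direction follows only if measurement error is shared, and the size is unknown. The fixed first position makes the baseline contrast harder to interpret, without a known direction. Sham vs intervention is unaffected in expectation.

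**What to change.** **Preferred.** Use the screening tasks for eligibility and arm choice only. After the eligibility decision, have every patient repeat the seven tasks without a device and use that recording as baseline, as second-visit patients already do. Task time is 7 × 30 s = 3.5 minutes per same-day patient, plus set-up and rating. Section 3 says the study has started, so this is an amendment to be notified to the ethics committee (Section 11.3). For patients already tested, report which kind of baseline was used. Re-measuring removes the regression to the mean. The confounding with time goes only if the no-device condition also joins the randomised sequence.

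**Otherwise.** Make sham vs intervention the confirmatory contrast on both endpoints, with two tests at 0.025, and label baseline vs intervention as supportive. This needs no new data. It does redefine the confirmatory family, so it must be fixed before the data are analysed. Power at n = 21 and dz = 0.8 is 0.88 instead of 0.81.

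**In either case.** Reword the Summary to say that only the sham/orthosis order is randomised, unless the no-device condition is added to the sequence.
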